6.2 PARTICIPANT DISCONTINUATION/WITHDRAWAL FROM THE STUDY

Participants can withdraw from the study at any time if they so wish. If a participant decides to withdraw their permission and disclosure of their Protected Health information from the study, she will need to do so in writing to the principal investigator [name] [name].

6.3 LOST TO FOLLOW-UP

Based on previous literature, we estimate that 50% of participants will complete their standard OGTT with reminders and incentives; the enrollment goals have been planned accordingly.

7 STUDY ASSESSMENTS AND PROCEDURES

7.1 ADVERSE EVENTS AND SERIOUS ADVERSE EVENTS

7.1.1 DEFINITION OF ADVERSE EVENTS (AE)

To ensure consistency of adverse event causality assessments, investigators will apply the following general guideline when determining whether an adverse event is related. An adverse event is considered related if there is a plausible temporal relationship between the onset of the adverse event and the study intervention, and the adverse event cannot be readily explained by the participant's clinical state, intercurrent illness, or concomitant therapies; and/or the adverse event follows a known pattern of response to the study intervention; and/or the adverse event abates or resolves upon discontinuation of the study intervention or dose reduction and, if applicable, reappears upon re-challenge.

An adverse event is considered unrelated if evidence exists that the adverse event has an etiology other than the study intervention (e.g., preexisting medical condition, underlying disease, intercurrent illness, or concomitant medication); and/or the adverse event has no plausible temporal relationship to study intervention.

7.1.2 DEFINITION OF SERIOUS ADVERSE EVENTS (SAE)

The intensity of adverse events will be rated on a three-point scale: (1) mild, (2) moderate, or (3) severe. It is emphasized that the term severe is a measure of intensity: thus, a severe adverse event is not necessarily serious. For example, itching for several days may be rated as severe, but may not be clinically serious.

Adverse events will be coded using the MedDRA dictionary.

All adverse events including adverse events that continue after the study participant's discontinuation or completion of the study will be followed until their medical outcome is determined or until no further change in the condition is expected.

Reporting Serious Adverse Events, Unexpected Adverse Device Effects

Any untoward occurrence that:

- Results in death.
- Results in transmission of a bloodborne pathogen.
- Is life-threatening; (a non-life-threatening event which, had it been more severe, might have become life-threatening, is not necessarily considered a serious adverse event).
- Requires inpatient hospitalization or prolongation of existing hospitalization.
- Results in persistent or significant disability/incapacity or substantial disruption of the ability to conduct normal life functions.
- Is a congenital anomaly or birth defect
- Is considered a significant medical event by the investigator based on medical judgment (e.g., may jeopardize the participant or may require medical/surgical intervention to prevent one of the endpoints listed above).

7.1.3 CLASSIFICATION OF AN ADVERSE EVENT

An Unanticipated Adverse Device Effect is defined as any serious adverse effect on health or safety or any life-threatening problem or death caused by, or associated with, a device, if that effect, problem, or death was not previously identified in nature, severity, or degree of incidence in the investigational plan or application (including a supplementary plan or application), or any other unanticipated serious problem associated with a device that relates to the rights, safety, or welfare of subjects.”

7.1.4 ADVERSE EVENT REPORTING

All unanticipated and/or adverse events will be reported to the IRB and sponsor.

8 STATISTICAL CONSIDERATIONS

8.1 SAMPLE SIZE DETERMINATION

This is a pilot study so previous data to inform sample size is limited. Group size is based on previous feasibility studies [19, 24]. The secondary outcomes will be used to develop preliminary data for power calculations for a future study powered to calculate accuracy of CGM testing compared to standard of care postpartum OGTT.

8.2 STATISTICAL ANALYSES

8.2.1 ANALYSIS OF THE PRIMARY EFFICACY ENDPOINT(S)

Percentage of participants with at least 72 hours of CGM data downloaded.

8.2.2 ANALYSIS OF THE SECONDARY ENDPOINT(S)

Specificity, sensitivity, PPV, and NPV for CGM compared to OGTT will be performed for diagnosis of DM, IGT, and IFG. Percentage of participants categorized as CGM-IFG, CGM-IGT and CGM-DM will be reported.

8.2.3 SAFETY ANALYSES

Percentage of participants with skin reactions will be reported.

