1.2 SCHEMA

1.3 SCHEDULE OF ACTIVITIES (SOA)

Visit	1	2	3	4	Home	5
Timing	Third trimester or 1-3 days postpartum	1-3 days postpartum	1-4 weeks postpartum	4-12 weeks postpartum	4-12 weeks postpartum 2-5 days before OGTT	4-12 weeks postpartum
Setting	In person or telehealth	Postpartum floor or telehealth	In person or telehealth	Telehealth		Telehealth or in person
Consent	X					
Medical history	X					
Pregnancy/Fetal outcome questions	X	X				
Professional sensor training	X	X		X		

Sensor placement		X			X	
Return of sensor			X			X
Skin assessment			X			X
Questionnaire			X			X
OGTT reminder call				X		

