2.3 RISK/BENEFIT ASSESSMENT

2.3.1 KNOWN POTENTIAL RISKS

Participants using the CGM will be at low risk for developing a local skin infection at the site of the sensor needle placement. If a catheter is left under the skin for more than 24 hours it is possible to get an infection where it goes into the skin, with swelling, redness and pain. There may be bleeding where the catheter is put in and bleeding under the skin causes a bruise (1 in 10 risk). In less than 1 out of 500 participants the CGM might break and leave a small portion of the sensor under the skin that may cause redness, swelling or pain at the insertion site.

Some participants may develop skin irritation or allergic reactions to the adhesives used to secure the CGM. If these reactions occur, different adhesives or "under-taping" (such as with IV 3000, Tegaderm, etc.) will be tried, sites will be rotated frequently, and a mild topical steroid cream or other medication may be required.

Whenever the skin is broken there is the possibility of an infection. The CGM sensors are inserted under the skin. It is possible that any part that is inserted under the skin may cause an infection. These occur very infrequently, but, if an infection was to occur, oral and/or topical antibiotics can be used.

Data downloaded from the CGM will be collected for the study as measures of diabetes self-management behaviors. Some people may be uncomfortable with the researchers' having such detailed information about their daily diabetes habits.

Loss of confidentiality is a potential risk; however, standard operating procedures will be followed as detailed in section 9.1.2 to minimize this risk.

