Visit 2: Visit 2 can be performed in conjunction with Visit 1 if the participant is already postpartum at recruitment or as a separate visit. It can be performed on the postpartum floor or remotely. The participant will be asked about pregnancy and delivery complications, GDM management, number of prenatal obstetric visits, estimated pregnancy weight gain, delivery weight and body mass index, gestational age at delivery, delivery method, steroid administration within the past week, fetal weight and complications, HbA1C values if available, and hemoglobin values. Participants will be asked for permission for access to review and record their future OGTT results. A Dexcom G6 Pro (or Dexcom G7 if FDA approved and available at the time of study) will be placed on an approved body site. The devices will be supplied by Dexcom at no cost to the subject. The participant will be trained on appropriate care of the sensor and removal.

Home use: Participants will wear the sensor for ten days or less if there is a sensor failure or the device is dislodged. After ten days, the participant will remove the sensor.

Visit 3: Visit 3 will occur 1-4 weeks after sensor placement. This visit can coincide with the participant's obstetrics or pediatric visit and can be performed in person or remotely. The participant will return the sensor at this visit, or mail the sensor to the study team within thirty days of placement. Postpartum complications and method of infant feeding obtained as part of normal postpartum care will be recorded. Participants will be asked whether they snack overnight and typical timing of breakfast, and the research team will determine what hour of the day would be considered fasting. If a participant is never fasting for over six hours, she will be considered to have not completed a fasting state. The investigator will assess for skin reaction at the sensor site. Participants will be asked about their experience and acceptability of blinded CGM. Participants will be encouraged to undergo the standard of care 6-12 week postpartum OGTT. Participants will be provided with another sensor to be placed before OGTT, and application will be reviewed.

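### Skin checks are not tied to sensor removal and the only safety result is an undefined skin-reaction percentage, so device-related events are likely to be under-reported

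*Combined protocol and SAP*

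**What the plan says.** **Analysis.** Section 8.2.3 reads in full: "Percentage of participants with skin reactions will be reported". It gives no definition, denominator, per-sensor rule or time window. Nothing else in section 8 summarises adverse events, serious adverse events or device effects.

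**First sensor.** Section 4.1 plans ten days of wear: "After ten days, the participant will remove the sensor". Wear may be shorter: "Participants will wear the sensor for ten days or less if there is a sensor failure or the device is dislodged". On timing, section 4.1 says "Visit 3 will occur 1-4 weeks after sensor placement", whereas the Schedule of Activities (1.3) gives "1-4 weeks postpartum" for the same visit. At that visit, "The investigator will assess for skin reaction at the sensor site". On its format: "This visit can coincide with the participant's obstetrics or pediatric visit and can be performed in person or remotely".

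**Second sensor.** The Schedule has it placed 2-5 days before the OGTT, and section 4.1 at least 48 hours before, again for ten days in total. Skin is assessed at Visit 5, which follows the OGTT and has no stated timing relative to removal.

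**Expected harms.** Section 2.3.1 lists site infection, bleeding, bruising ("bleeding under the skin causes a bruise (1 in 10 risk"), adhesive irritation or allergy, and sensor breakage in fewer than 1 in 500.

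**Adverse event handling.** Section 7.1 has adverse events assessed for relatedness, graded for intensity, coded in MedDRA, followed to outcome and reported to the IRB and sponsor.

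**The concern.** A device proposed for screening women soon after delivery will be judged partly on what it does to them. The single planned safety figure depends on when someone looks and on what that person calls a skin reaction, and the plan fixes neither. A check made while the sensor is still on cannot see what happens during the rest of wear or at removal. A check made weeks after removal may miss a reaction that has settled; the protocol's own example of a severe but non-serious event, in section 7.1.2, is itching that lasts some days. No instruction tells staff to ask about reactions since placement.

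Two sites, or two staff members, could follow the plan exactly and report different rates from the same experience. Events already coded under section 7.1 would not reach the safety result at all.

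**Working it through.** The plan gives no computed safety figure, and section 8.1 bases the 50 participants on earlier feasibility studies, so there is no figure to reproduce. The check is date arithmetic plus expected counts.

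**1. Visit 3 against removal, section 4.1 wording.** Visit 3 is day 7 to day 28 after placement; removal is day 10.
- Earliest: 7 − 10 = −3, that is, 3 days before removal.
- Latest: 28 − 10 = +18, that is, 18 days after removal.
- If wear ends early, for example at 72 hours, the latest gap is 28 − 3 = 25 days.

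**2. Visit 3 against removal, Schedule wording.** Visit 3 is day 7 to day 28 postpartum. Placement is postpartum day 0-3 in section 4.1 (day 1-3 in the synopsis and Schedule), so removal is day 10-13.
- Earliest: 7 − (3 + 10) = −6.
- Latest: 28 − (0 + 10) = +18, or 28 − (1 + 10) = +17 if placement starts at day 1.

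**3. Visit 5 against removal.** With placement 2-5 days before the OGTT and ten days of wear:
- placed 2 days before: 10 − 2 = 8 days after the OGTT;
- placed 5 days before: 10 − 5 = 5 days after the OGTT.

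A Visit 5 held within 5 to 8 days of the OGTT can therefore precede removal, and nothing in the plan prevents that. There is also no latest date.

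**4. Expected events at the protocol's own risks, N = 50, read as per participant.**
- Bruising: 50 × 0.10 = 5 women. P(at least one) = 1 − 0.9^50 = 99.5%. If 5 of 50 were seen, the Clopper-Pearson 95% interval is 3.3% to 21.8%.
- Breakage: at most 50/500 = 0.1 events. P(at least one) ≤ 1 − 0.998^50 = 9.5%. This is too rare to move a percentage here.

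**5. What turns on the definition.** The documents give no skin-reaction rate, so a range is assumed, with bruising at 10% and independent. Any skin reaction or bruise = 1 − (1 − s) × 0.9, and the share shown if bruises are left out = s divided by that.

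| Assumed skin-reaction rate s | Reaction or bruise | Share shown without bruises |
|---|---|---|
| 2% | 11.8% | 17% |
| 5% | 14.5% | 34% |
| 10% | 19.0% | 53% |
| 20% | 28.0% | 71% |

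These shares assume every reaction is detected. They apply only if bruising is read as outside the term.

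**6. Denominator.** Section 6.1 withdraws women not willing or able to wear the device for 72 hours. Section 5.5 drops the data of anyone who meets an exclusion criterion after enrolment, and known adhesive allergy is one (section 5.3). Section 8.2.3 does not say whether such women still count for safety. Section 6.1 also lets a woman with a skin reaction and 72 hours of data forgo the second sensor, so second-sensor wearers are selected for tolerance and the two sensors should be reported separately.

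**The case against.** The strongest reply is that little is lost. This is a 50-woman feasibility pilot with no safety objective in section 3, and no decision depends on section 8.2.3. Acceptability has its own endpoint. Sections 2.2 and 4.1 plan sensor return at about two weeks; on day 14 postpartum that is 14 − 13 = 1 to 14 − 10 = 4 days after removal, a sensible time to look. A Visit 3 before removal also sits badly with returning the sensor at that visit, unless it is mailed. All of this stands, and it keeps the point minor. It does not close the gap, because the stated windows permit the extremes.

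Four stronger readings are tempting, and the documents do not support them:
- *Skin is looked at only once.* It is assessed at both Visit 3 and Visit 5, once per sensor.
- *Bruising and infection are excluded.* Section 2.3.1 uses the word reactions for adhesive problems and treats bruising separately, which favours a narrow reading. But the term is undefined, and a bruise or infected site is a visible skin change.
- *These harms go uncaptured.* Section 7.1 covers all adverse events. What is missing is a planned summary.
- *Harm will certainly read too low.* No healing time is given, and no rule limits the check to signs visible that day. Women are asked about their experience and may mention past reactions, and a remote check may rest on their account.

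A reader might also infer 7 or 8 bruises, from 75 sensors × 0.10 = 7.5. That needs the risk to be per insertion, which section 2.3.1 does not say. It also needs half the women to wear a second sensor, but the 50% estimate concerns OGTT completion, and all participants are told to place one.

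**Conclusion.** The point holds as a minor one. Neither skin check is tied to removal. The Visit 3 check can fall from 3 days before removal (6 on the Schedule's wording) to 18 days after it with full wear, and Visit 5 can also come before removal. The only planned safety result rests on an undefined term and has no stated denominator, and it draws nothing from the adverse events that section 7.1 already codes.

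Under-reporting of device-related events is the likely direction, but it is not demonstrated. Its size cannot be fixed from the documents. The one usable anchor is about 5 bruises in 50 women, which assumes that the 1 in 10 risk is per participant; whether section 8.2.3 would count them depends on how the term is read.

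**What to change.** 1. At Visits 3 and 5, count any site reaction the woman reports since placement as well as what is seen.
2. Reconcile the two Visit 3 windows with each other, and the Visit 3 and Visit 5 timing with the ten-day wear, so that each count covers the whole wear period.
3. In section 8.2.3, define skin reaction and report device-related events by type (skin reaction, bleeding or bruising, infection, retained sensor part), per woman and per sensor. Use the adverse events already collected, with all women who had a sensor placed as the denominator, whether or not they were later withdrawn.

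The cost is SAP wording and one added question at existing visits. Recalled events are less precise than observed ones, so seen and reported events should be distinguishable in the table. The reported rate will probably be higher.

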8.2.4 EXPLORATORY ANALYSES

A secondary analysis will be performed in which we remove any data within 4 half-lives of last known steroid exposure.

CGM data from 4-12 weeks postpartum will be compared to the immediate postpartum CGM data and to the postpartum OGTT.

Sensitivity and specificity of DM, IGT, and IFG for sensor worn at the time of postpartum OGTT will be explored.

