1 PROTOCOL SUMMARY

1.1 SYNOPSIS

Title:	Postpartum dysglycemia screening with continuous glucose monitoring
Study	Gestational diabetes (GDM) is one of the most common complications of pregnancy, and up to one third of women with GDM will have abnormal blood sugars after their pregnancy. To screen for abnormal blood sugars, standard of care is a 6-12 week postpartum oral glucose tolerance test (OGTT). However only 17-60% of women actually have this test performed. This study is to assess the feasibility of using a continuous glucose monitor placed on discharge from the hospital after delivery as a screening method to detect postpartum abnormal blood sugars.
Description:	
Objectives:	
Primary Objective: To assess the feasibility of continuous glucose monitoring compared to oral glucose tolerance testing for the diagnosis of postpartum diabetes in women with recent gestational diabetes.
 
Secondary Objectives: To evaluate the specificity, sensitivity, positive predictive value, and negative predictive value of continuous glucose monitoring compared to oral glucose tolerance testing for the diagnosis of postpartum dysglycemia in women with recent gestational diabetes.
 
To evaluate the influence of predictors of lack of postpartum oral glucose tolerance testing on completion of postpartum continuous glucose monitoring.

Endpoints:	
Primary Endpoint: Percentage of participants with at least 72 hours of CGM data downloaded.
 
Secondary Endpoints: CGM acceptability scoring Specificity, sensitivity, PPV, and NPV for CGM compared to OGTT will be performed for diagnosis of DM, IGT, and IFG

Study Population:	Pregnant or recently pregnant women who were diagnosed with GDM during current/recent pregnancy. Target enrollment: 50 participants
Sites/Facilities Enrolling Participants:	Icahn School of Medicine at Mount Sinai

[figure not shown]

Description of Study Intervention: Women will be consented and screened before or after delivery. They will be asked about medical history, medications, and diabetes risk factors. A Dexcom Professional CGM will be placed on postpartum day 1-3. Participants will wear the sensor for 10 days and return it at their postpartum visit or by mail. They will be given another sensor to place before their standard of care OGTT and will mail the sensor back after that test is performed.

Study Duration: 1 years

Participant Duration: Up to 20 weeks

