Standard of care for postpartum screening is not met by the majority of women who are at high risk to continue to have dysglycemia. Screening for diabetes and IGT using a 75-g, 2 hour OGTT is recommended by obstetric and endocrinology societies including ADA, ACOG, and WHO at 6-12 weeks postpartum [1-3, 8]. Unfortunately, postpartum screening at this time only occurs in 17-60% of women even during studies designed to promote testing [9-11]. In a randomized control trial, Clark et al found that postal reminders to patients and physicians led to an increase in screening by one year postpartum with 14.3% tested by one year with no reminder, 51.6% with a reminder to the physician, 55.3% with reminder to patient, and 60.5% with reminder to physician and patient ($p<0.05$) [5]. Implementation of this strategy at two Canadian hospital systems did increase rates of screening, but not as robustly as seen in the original randomized control trial described above [9], with 28% OGTT completion by 6 months with reminders compared with 14% completion with usual care ($p=0.1$) [12]. The DIAMIND study in Australia found that a reminder at six weeks did not increase screening by six months postpartum [13]. Multiple interventions have been studied at Mount Sinai Hospital: after implementation of an advanced order set at the 35-week pregnancy visit, provider education modules, and nutritionist phone calls reminding patients to fast before postpartum testing, OGTT test completion in association with a six week postpartum visit increased from 17% to 36% ($p=0.01$) [10].

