3 OBJECTIVES AND ENDPOINTS

OBJECTIVES	ENDPOINTS	JUSTIFICATION FOR ENDPOINTS
Primary To assess the feasibility of continuous glucose monitoring compared to oral glucose tolerance testing for the diagnosis of postpartum diabetes in women with recent gestational diabetes.	Percentage of participants with at least 72 hours of CGM data downloaded.	72 hours of data has been accepted as sufficient for identifying CGM trends
Secondary To evaluate the specificity, sensitivity, positive predictive value, and negative predictive value of continuous glucose monitoring compared to oral glucose tolerance testing for the diagnosis of postpartum dysglycemia in women with recent gestational diabetes.	CGM acceptability scoring Specificity, sensitivity, PPV, and NPV for CGM compared to OGTT will be performed for diagnosis of DM, IGT, and IFG	Of participants who receive standard of care, the CGM data will be compared to the standard of care to assess specificity, sensitivity, PPV, and NPV
Tertiary/Exploratory Association of risk factors with nonadherence to postpartum OGTT. A secondary analysis will be performed in which we remove any data within 4 half-lives of last known steroid exposure. Sensitivity and specificity of DM, IGT, and IFG for sensor worn at the time of postpartum OGTT will be explored.	Demographics, CGM return, OGTT completion Specificity, sensitivity, PPV, and NPV for CGM compared to OGTT will be performed for diagnosis of DM, IGT, and IFG excluding data within 4 half-lives of last known steroid exposure. CGM data from 4-12 weeks postpartum will be compared to the immediate postpartum CGM data and to the postpartum OGTT.	Demographic data will be analyzed to assess if similar populations complete CGM vs OGTT Steroids affect blood sugar. This exploratory analysis will help to determine if this needs to be considered when using CGM to assess for postpartum dysglycemia. Stability of CGM trends over the postpartum weeks will be assessed, and CGM data from the same time as OGTT will be compared.

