Visit 4: Visit 4 will be conducted remotely. Participants will be contacted by text or phone call to encourage them to undergo the standard of care OGTT. If a participant is unable to have an OGTT performed through her normal care, she can have an optional in-person visit to have it performed at the study site. All participants will be instructed to place a Dexcom sensor at least 48 hours prior to their planned OGTT.

Home use: Participants will wear the sensor for at least 48 hours before planned OGTT for a total of ten days or less if there is a sensor failure or the device is dislodged. After ten days, the participant will remove the sensor.

Visit 5: Visit 5 will be conducted remotely after the 6-12 week OGTT. Participants will be instructed to mail the sensor back to the study team in pre-addressed, prepaid packaging. The investigator will assess for skin reaction at sensor site. Participants will be asked about their experience and acceptability of OGTT testing. Results of the OGTT will be recorded. If it is performed at an outside facility, the participant will request that the records be shared with the research team. Results of CGM data may be shared with a participant and her providers if requested by the participant after her routine OGTT. Investigators will not provide results before this to decrease risk of participants not completing the standard of care OGTT.

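### Section 8.2.4 does not set aside the OGTT hours in the second-sensor record, so the reference test's glucose load can influence the late CGM-DM and CGM-IGT classes and the early-versus-late comparison

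*Combined protocol and SAP*

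**What the plan says.** Section 8.2.4 plans two analyses of the second sensor. One is an accuracy analysis against the OGTT: "Sensitivity and specificity of DM, IGT, and IFG for sensor worn at the time of postpartum OGTT will be explored". The other sets the late record beside both the early record and the OGTT: "CGM data from 4-12 weeks postpartum will be compared to the immediate postpartum CGM data and to the postpartum OGTT".

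The wear schedule puts the OGTT inside that record. Section 4.1 (second home-use period) says: "Participants will wear the sensor for at least 48 hours before planned OGTT for a total of ten days", allowing less if the sensor fails or comes off. The schedule of activities (section 1.3) places the sensor 2-5 days before the test. The synopsis adds that participants "will mail the sensor back after that test is performed". Section 2.2 describes the test: "Screening for diabetes and IGT using a 75-g, 2 hour OGTT is recommended".

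The only CGM data exclusion written in 8.2.4 concerns recent steroid exposure. The justification column in section 3 adds that "CGM data from the same time as OGTT will be compared". At Visit 5 (section 4.1), "Results of the OGTT will be recorded"; no start time is listed. For tests done elsewhere: "If it is performed at an outside facility, the participant will request that the records be shared with the research team".

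CGM-IFG, CGM-IGT and CGM-diabetes appear in section 8.2.2 and the abbreviations list, but no numeric rule for any of them is given.

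**The concern.** The study asks whether a CGM profile from ordinary living could stand in for an OGTT that many women never have. A woman screened by CGM alone would have no 75-g load in her record. In the second wear every woman who is tested has one, and it is the same challenge that sets her reference class. A woman with a large response to the drink raises her own sensor readings during the test, so a class built on time above range, mean or peak is pulled toward the OGTT result.

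The early record contains no load. If the late record keeps its load, part of any early-versus-late difference reflects the test and not change over the postpartum weeks. Section 3 gives stability of CGM trends as a purpose of that comparison.

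The plan already accepts, for steroids, that a known disturbance of glucose can justify removing data. It does not address the one that it schedules itself.

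**Working it through.** The documents state no figure for this point, so there is none to reproduce. The check is the share of the record taken up by the test, set against the plan's own healthy benchmarks.

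**Inputs from the documents**
- Planned wear: 10 days × 24 = 240 h (section 4.1).
- Test length: 2 h (section 2.2).
- Healthy time above threshold (section 2.2): above 180 mg/dL, median 0%, upper quartile 0.2%; above 160, 0.3% and 0.9%; above 140, 2.1% and 3.9%.
- Expected OGTTs: 50 × 50% = 25 (sections 5.1, 5.6 and 6.3).

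**Assumption:** h, the hours above the threshold caused by the load, ranges from 0.5 to 2 h, with 4 h as an extended case.

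**Step 1: is the test inside the record?** With a lead of 2-5 days, the test starts 48 to 120 h into a 240 h wear. It is inside.

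**Step 2: share of the record**
- 2/240 = 0.83%.
- 4/240 = 1.7%.
- If the sensor were lost or removed early, leaving a 72 h record: 2/72 = 2.78%.
- If it came off straight after the test with a 48 h lead: 2/50 = 4.0%.

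**Step 3: effect on time above threshold.** Take a woman otherwise at the healthy median m, over 240 h with a window of w hours:

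percent above = [m × (240 − w) + 100 × h] / 240, with m in percent

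| Threshold | h = 0.5 (w = 2) | h = 1 (w = 2) | h = 2 (w = 2) | h = 4 (w = 4) | Healthy upper quartile |
|---|---|---|---|---|---|
| 180 mg/dL | 0.21% | 0.42% | 0.83% | 1.67% | 0.2% |
| 160 mg/dL | 0.51% | 0.71% | 1.13% | 1.96% | 0.9% |
| 140 mg/dL | 2.29% | 2.50% | 2.92% | 3.73% | 3.9% |

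Example: above 160 with h = 2, (0.3 × 238 + 200)/240 = 271.4/240 = 1.13%.

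Above 180 the healthy upper quartile is 0.002 × 240 = 0.48 h, so about half an hour of excursion is enough to pass it. Above 140 the record stays within the healthy range even at 4 h. In a 72 h record with h = 2, the figure above 140 is (2.1 × 70 + 200)/72 = 4.82%, which passes 3.9%.

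**Step 4: mean and peak.** If glucose over a 4 h window averages X mg/dL above the rest of the record, the overall mean rises by X × 4/240 = X/60, which is small. A peak-based rule (an assumption) could be decided by the test alone.

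**Step 5: after removal.** The same woman returns to 0%, 0.3% and 2.1%, provided that the window covers the whole excursion.

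**The case against.** The strongest reply is that using the OGTT hours is intended. Section 3 says that "CGM data from the same time as OGTT will be compared", and two methods measuring one challenge is a legitimate agreement question. The phrase could mean the in-test hours or merely the same weeks. On either reading an in-test comparison can stand as its own analysis. Nothing in the plan separates it from classification of the everyday profile, and that separation is what is missing.

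The stakes are also low. These analyses are exploratory, with no hypothesis or decision attached, and section 8.1 bases future power calculations on the secondary outcomes. With about 25 OGTTs and up to one third abnormal (section 2.2), roughly 8 cases are expected. As an illustration, 6 of 8 detected has an exact 95% interval of about 35% to 97%, so a shift in classes would be hard to see. This stands, and it limits the weight of the point.

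Four stronger readings are tempting, and the documents do not support them:
- **The load certainly changes the CGM class.** That depends on a classification rule that is not given.
- **All three classes are affected.** At Visit 3 (section 4.1) the team sets each woman's fasting hours. CGM-IFG would rest on such hours, which precede the drink.
- **The test fills several percent of the record.** Mailing the sensor back after the test does not mean removing it then, since section 4.1 plans ten days of wear. Shares such as 2.78% or 4.0% need early loss or removal.
- **The comparison is fully circular.** Blood and sensor values are separate measurements that share a stimulus, and the sensor does not define the reference class.

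Nor is 0.83 percentage points a ceiling on the effect. A woman whose 2 h value is raised remains raised for some time afterwards.

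**Conclusion.** The point holds as a conditional one. Followed as written, the plan lets the load of the reference test feed the late CGM metrics, both when the second sensor is scored against that OGTT and when it is compared with an early record that has no load. The likely direction is toward better agreement for DM and IGT, plus a late-only addition to time above range.

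Under planned wear the test hours are under 2% of the record, even with a 4 h window. That is minor for time above 140 mg/dL, material for time above 180 mg/dL, and potentially decisive under a peak rule. The quartiles used above describe healthy volunteers and are not diagnostic cut-offs, so they show scale and not misclassification.

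The primary endpoint is untouched. So is the accuracy analysis in 8.2.2, read as concerning the first sensor because 8.2.4 treats the second one separately. This is an improvement to consider, not an error that threatens the study's main results.

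**What to change.** In section 8.2.4:

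1. Derive second-sensor CGM-DM and CGM-IGT classes, and all early-versus-late metrics, after removing the hours from the glucose drink to a fixed time after it. Four hours is a reasonable example (an assumption), because excursions can outlast the 2 h test.
2. Keep the fasting hours before the drink for CGM-IFG. They are the hours best matched to the fasting OGTT sample.
3. Report sensor readings during the test against the OGTT glucose values as a separate paired comparison.

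In section 4.1, Visit 5: record the OGTT date and start time. If only the date is known, remove that day's data from the woman's usual breakfast time onward (already asked at Visit 3), not the whole day.

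**Cost:** a few lines of text, one extra data item and no new visit. About 4 h is lost per record (1.7% of 240 h). Under the date-only fallback the loss is more, but less than 24 h (10%). Start times from outside facilities may take some effort to obtain and are easiest to collect prospectively.
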